## 5.0 Inclusion and Exclusion Criteria/ Study Population

Participants will be recruited from an MUSC database containing the contact information of stroke survivors who have agreed to be contacted for research participation (Pro00037803). Initial screening will be performed by study staff through a phone call to confirm basic participant characteristics (e.g. timing of stroke) and interest in research participation. The ability of potential participants to meet the more detailed inclusion and exclusion criteria will subsequently be determined in person.

### Inclusion Criteria

- Age  $\geq$  21 years
- Experience of a stroke  $\geq$  6 months prior to participation
- Gait speed of at least 0.2 m/s
- Ability to walk on a treadmill without a cane or walker
- Provision of informed consent

### Exclusion Criteria

- Evidence of cerebellar damage
- Resting blood pressure higher than 220/110 mm Hg
- History of unstable cardiac arrhythmias, hypertrophic cardiomyopathy, severe aortic stenosis, angina or dyspnea at rest or during activities of daily living
- Preexisting neurological disorders or dementia
- Legal blindness or severe visual impairment
- History of DVT or pulmonary embolism within 6 months
- Uncontrolled diabetes with recent weight loss, diabetic coma, or frequent insulin reactions
- Orthopedic injuries or conditions (e.g. joint replacements) in the lower extremities with the potential to alter the gait pattern
- Recent (within last 6 months) Botox injections in the hip musculature

We plan to include a diverse participant population, paralleling the general demographic characteristics of the Charleston area. This will be accomplished using the database referenced above, which currently contains contact information for over 800 individuals. We will not exclude any sex/gender or racial/ethnic group. This study will not involve any special classes of subjects, including fetuses, neonates, pregnant women, children, prisoners, institutionalized individuals, or other vulnerable populations. Children will not be included because this study focuses on individuals who have experienced a stroke. This is rare among children, and would be expected to involve a quite different mechanism or pattern of recovery.

## 6.0 Number of Subjects

A total of 120 chronic stroke survivors will be accrued, all locally.

## 7.0 Setting

All research will be performed in the MUSC College of Health Professions Research Building at [name].

## 8.0 Recruitment Methods

This study will recruit from the Registry for Stroke Recovery (RESTORE-Pro#00037803, IRB approved 9/6/14), which is a research tool sponsored by the National Institutes of Health (NIH) Center of Biomedical Research Excellence (COBRE) in Stroke Recovery with subjects consented for future contact to support stroke recovery research conducted at MUSC. RESTORE staff will query the registry for potential subjects and provide the Principal Investigator (PI) with the contact information of subjects who meet their criteria. The PI or research staff will contact subjects to further screen for potential enrollment.

Additionally, we have developed a study flyer that will be shared through the COBRE and distributed through stroke support groups attended by study personnel.

## 9.0 Consent Process

Informed consent will be obtained from participants prior to participation, using a VA Informed Consent form approved by the MUSC IRB. Participants will first be informed of the purpose of the experiments and possible risks. A member of the study staff will then review the Informed Consent form with the potential participant, ensuring they are given adequate time to review the document. The potential participant will be asked if they have any questions about the study, and asked if they agree to participate. The Informed Consent form will be signed by the participant. Copies of the signed forms will be given to the participant. The consent process will take place in a private room in the MUSC College of Health Professions Building. There will be no set period between informing the prospective participant and obtaining the consent. Participants will be reminded that they may end their participation in the study at any point.

## 10.0 Study Design / Methods

A total of 120 chronic stroke survivors will be recruited for an initial Screening session to determine eligibility for enrollment in the subsequent Aims. From this initial session, 40 stroke survivors will be recruited for Aim 1, and a separate 40 stroke survivors will be recruited for Aim 2. From these 80 participants in Aims 1 and 2, a total of 44 will be recruited for Aim 3. Aim 1 involves a single-session experiment, Aim 2 involves two experimental sessions, while Aim 3 involves an intervention with a total of 10-11 sessions. Participants will be enrolled in this study for a period of a year, allowing time to complete all potential sessions.

In the initial Screening session, participants will walk on an instrumented treadmill for 2-minutes. We will calculate  $\rho_{\text{disp}}$  (a measure of the typical gait stabilization strategy) using LED markers and inertial measurement units placed over participants' legs and pelvis. If  $\rho_{\text{disp}}$  is less than 0.56 (well below control norms), participants will qualify to progress to the subsequent Aims. During the Screening session, we will also quantify the secondary

measures of: Functional Gait Assessment; Activities-specific Balance Confidence scale, Fugl-Meyer Lower Extremity Motor Function subscale; Fugl-Meyer Lower Extremity Sensation subscale; self-selected and fastest-comfortable overground gait speed; fear of falling; fall history. All of these secondary measures are commonly used in clinical practice.

In Aim 1, participants will complete a single-session experiment. We will quantify the cutaneous detection threshold for vibration delivered over the bilateral hip abductors. We will also calculate the lateral sway evoked by vibration of each leg, quantified as the shift in center of pressure while standing on a force plate. Participants will then perform a series of treadmill walking trials. In some of these trials, vibration will be applied to the hip abductors or lateral trunk, while we quantify  $\rho_{\text{disp}}$ .

In Aim 2, participants will complete two experimental sessions. In the first session, participants will perform a series of treadmill walking trials, across which we will vary the pattern and location of vibration applied over the bilateral hip abductors. We will identify the combination of pattern and location that produces the largest increase in  $\rho_{\text{disp}}$  for each participant. In the second session, participants will again perform a series of treadmill walking trials, across which we will compare the personalized stimulation (optimal pattern and location for this individual) with the standard pattern of stimulation used in prior work.

In Aim 3, participants will complete 10-11 experimental sessions. The first and last session will consist of pre and post assessments, in which we will quantify  $\rho_{\text{disp}}$ , Functional Gait Assessment score, Activities-specific Balance Confidence score, overground self-selected and fastest-comfortable walking speeds, and fear of falling. If Aim 2 reveals that personalized stimulation is superior to standard stimulation, the second session will be used to identify the optimal combination of stimulation pattern and location for each participant. Otherwise, this session will not be performed. The remaining sessions will be training sessions, in which participants will perform a series of walking trials at their self-selected speed. In some trials, hip abductor vibration will be applied on a step-by-step basis. In the Augmented group, this vibration will be scaled to augment sensory feedback providing information about the mechanical state of the pelvis. In the Control group, the magnitude of this vibration will be randomized, providing no additional information.

To reduce the risk of participants falling, participants will wear a harness attached to an overhead rail during all treadmill and overground walking trials. This harness will not support body weight, but would prevent participants from falling in the case of a loss of balance. The vibrating tactors and adhesive used to secure the tactors and LED markers to the skin may produce the risk of minor skin irritation. We will reduce this risk by asking participants if they have had any previous experience of skin irritation in reaction to specific gel or tape types, and by checking the participants' skin after each experiment.

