### 4.0 Study Endpoints

For the intervention in Aim 3, our outcome measure of safety will be the proportion of participants who experience an adverse event potentially related to the intervention (e.g. skin irritation; falls) or any serious adverse event (e.g. hospitalization; death). Our primary measures of feasibility will be participant adherence (percentage of training sessions attended) and drop-out (non-attendance of final assessment session). We will also track the total walking time across training sessions (of a maximum possible 312 minutes). Our primary measure of efficacy will be changes in  $\rho_{\text{disp}}$ , a metric that quantifies the extent to which participants effectively stabilize their gait by adjusting their step width to account for pelvis dynamics [20]. Our secondary measures of efficacy will be the common clinical measures of Functional Gait Assessment score, Activities-specific Balance Confidence score, overground gait speed, and fear of falling.

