## 12.0 Provisions to Monitor the Data to Ensure the Safety of Subjects

A Data Safety Monitoring Board (DSMB) will oversee the experiments in Aim 3 (a small-scale randomized controlled trial). This board will consist of a neurologist, a statistician,

and an experienced rehabilitation researcher (all with no direct ties to this study). On a quarterly basis, the DSMB will review the status of the study. The role of the DSMB will be to:

- Protect the safety of study participants
- Review the research protocol, informed consent documents, amendments, and plans for data safety and monitoring
- Evaluate the progress of the trial, including periodic assessments of data quality and timeliness, recruitment, accrual, and retention, participant risk vs. benefit, and other factors that may potentially affect study outcome
- Review study performance, make recommendations and assist in the resolution of problems reported by the Principal Investigator
- Report to the IRB on the safety and progress of the trial
- Ensure the confidentiality of the study data and the results of the monitoring
- Advise the IRB and the study investigators as to whether the protocol should continue as scheduled or undergo a modification due to a finding from the monitoring process

Any adverse events will be recorded, monitored, and promptly reported to the IRB, following policy HRPP 4.7. Our exclusion criteria will minimize the risk of enrolling participants with severe cardiovascular risk. Scheduled rest breaks will be provided between trials during experimental testing, as well as whenever requested. Minimization of risk of adverse events will be accomplished by monitoring vital signs during trials in which subjects are performing potentially demanding exercise. Collected data and any events potentially affecting participant safety will be reviewed by the principal investigator after each data collection session.

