## **13.0 Withdrawal of Subjects**

Participants will be withdrawn from the study without their consent if study staff determine that the participants are at risk of negative health events (e.g. large increase in blood pressure from the initial screening assessment; consistent inability to maintain balance while walking on the treadmill). If a participant voluntarily withdraws from the study, their results will not be included in our data analysis, as our intervention sample size accounts for 20% dropout.

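### Aim 3 safety is measured only in people already exposed to vibration in Aims 1 or 2, so it does not describe first exposure and may understate risk in unselected stroke survivors

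*Combined protocol and SAP*

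**What the plan says.** All references are to the combined protocol and SAP.

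- **Entry to Aim 3 (section 10.0).** Forty people are recruited to Aim 1 and a separate 40 to Aim 2. Then: "From these 80 participants in Aims 1 and 2, a total of 44 will be recruited for Aim 3". No other way in is described, and no rule says how the 44 are picked.
- **Exposure before Aim 3 (section 10.0).** In Aim 1, "In some of these trials, vibration will be applied to the hip abductors or lateral trunk". Aim 2 has two sessions of walking trials, the first described as trials "across which we will vary the pattern and location of vibration applied over the bilateral hip abductors".
- **Safety outcome (section 4.0).** "For the intervention in Aim 3, our outcome measure of safety will be the proportion of participants who experience an adverse event", where the event is possibly related to the intervention (skin irritation and falls are the examples), or any serious event.
- **Oversight (section 12.0).** "A Data Safety Monitoring Board (DSMB) will oversee the experiments in Aim 3 (a small-scale randomized controlled trial". Two further provisions are not limited to Aim 3: "Any adverse events will be recorded, monitored, and promptly reported to the IRB, following policy HRPP 4.7", and "Collected data and any events potentially affecting participant safety will be reviewed by the principal investigator after each data collection session".
- **Withdrawal (section 13.0).** "Participants will be withdrawn from the study without their consent if study staff determine that the participants are at risk of negative health events". This applies to the whole study. The same section leaves the results of voluntary withdrawals out of the analysis and states no exception for safety.
- **Goal (section 3.0).** The project intends to settle the safety of the intervention definitively.

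**The concern.** A safety proportion for a new intervention is normally read as the risk for someone about to start it. Here nobody counted is about to start. Each Aim 3 participant has already worn the tactors and walked with vibration, and has then gone on to a longer study. Whatever happened the first time is not part of the figure.

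Randomisation does not repair this. Both Aim 3 groups are drawn from the same 80 people, and under section 3.0 the Control group also receives hip abductor vibration.

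Two things are at stake. The first is interpretation: a low proportion could be presented as the risk for chronic stroke survivors in general, when it belongs to people who had earlier exposure and continued. The second is oversight: the independent board begins its work on Aim 3 with no stated entitlement to the events already seen with the same device in up to 80 people.

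**Working it through.** **1. The plan's own figure.** Section 11.0 gives 17 per group for an effect size of 1.0, alpha 0.05 and power 0.80, and 22 per group after 20% dropout. A two-sided two-sample t-test gives 16.7, so 17 per group (power 0.807). Then 17 / 0.80 = 21.25, so 22, and 2 × 22 = 44. The figure reproduces, but it rests on efficacy. No sample-size basis is given for the safety proportion.

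**2. Who is counted.** 44 / 80 = 55% enter Aim 3 and 80 − 44 = 36 do not. Part of that 36 is simply the cap of 44, so it is not a measure of loss for safety reasons.

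**3. Where a first-exposure event in Aim 1 or 2 goes.**

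| Destination | Covered? | Section |
|---|---|---|
| Record and IRB report | Yes | 12.0 |
| Principal investigator review | Yes | 12.0 |
| Safety outcome | No, Aim 3 only | 4.0 |
| DSMB | Not in its stated assignment | 12.0 |

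**4. When selection lowers the Aim 3 figure.** Let *s* be the event-prone share among the 80, and *r* the chance that such a person enters Aim 3 relative to anyone else. The event-prone share in Aim 3 is

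share = *s·r* / (*s·r* + 1 − *s*).

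The documents give neither *s* nor *r*, so both are assumed. For *s* = 10%:

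| *r* | Calculation | Aim 3 share | Expected among 44 |
|---|---|---|---|
| 1 | 0.100 / 1.000 | 10% | 4.4 |
| 0.75 | 0.075 / 0.975 | 7.7% | 3.4 |
| 0.5 | 0.050 / 0.950 | 5.3% | 2.3 |
| 0.25 | 0.025 / 0.925 | 2.7% | 1.2 |
| 0 | 0 / 0.900 | 0% | 0 |

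At *r* = 0.5, *s* = 5% gives 0.025 / 0.975 = 2.6%, and *s* = 20% gives 0.10 / 0.90 = 11.1%. At *r* = 1 there is no selection bias for any *s*. The model treats proneness as a fixed trait and ignores differences in exposure time.

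**5. Is *r* below 1 plausible?** For anyone withdrawn by staff during Aim 1 or 2, *r* = 0, because withdrawal is from the study as a whole. One of the examples in section 13.0, persistent loss of balance on the treadmill, is close to falls, which section 4.0 names as a safety event. People who had irritation may also decline the 10 to 11 sessions of Aim 3, although the documents do not say so.

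**6. What the unused data could add.** With no events in *n* people, the one-sided 95% upper limit is 1 − 0.05^(1/*n*): 6.6% for *n* = 44 and 3.7% for *n* = 80. These answer different questions (repeated training against first exposure), so they belong side by side, not pooled.

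**7. Voluntary withdrawals.** Suppose 9 of 44 withdraw (20% of 44 is 8.8) and, with assumed counts, 2 of the 35 who remain and 2 of the 9 have an event. Dropping the 9 reports 2/35 = 5.7%; counting everyone gives 4/44 = 9.1%.

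**The case against.** The strongest reply is that Aim 3 asks a different question. Section 1.0 frames it as the safety of repeated exposure, and section 3.0 says that Aims 1 and 2 contain no intervention. Aim 3 allows up to 312 minutes of training walking, so its event proportion could exceed that of one or two earlier sessions. The earlier exposure also differs in kind: Aim 1 includes trunk vibration and standing sway tests, and Aim 2 varies pattern and location. This stands, and it is why first-exposure events should not be merged into the randomised Aim 3 outcome. It does not make the Aim 3 figure a description of first exposure.

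A reader might infer that the proportion simply is biased low. The documents do not support that as fact. They give no event rates, no return rates, no rule for choosing the 44, and no bar for an earlier event. Being withdrawn as at risk is not itself an adverse event. Section 14.0 expects skin irritation to clear within a day, which does not suggest that everyone affected would be lost. Screening already includes a treadmill walk, so some selection on balance would occur without Aims 1 and 2.

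A reader might also set 0/44 (exact 95% upper limit 8.0%) against 8/80 = 10.0% (4.4 to 18.8%). That contrast assumes that all eight people with an event fail to enter Aim 3. If four of the 80 were event-prone and the 44 were drawn at random, the chance that none of the four was included would be only 3.7%.

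Nor are Aim 1 and 2 events unmonitored, given the recording, IRB reporting and investigator review in section 12.0. The board's quarterly look at the status of the study leaves some room for it to see them. What is missing is an explicit assignment and a place in the reported results.

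**Conclusion.** The point holds in two parts of different strength.

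By design, and without further assumption, the Aim 3 safety proportion applies to previously exposed people who went on to Aim 3. It does not describe first exposure, and it cannot carry the definitive safety claim that section 3.0 sets as a goal. For that narrower population, this selection introduces no bias.

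Conditionally, the proportion may be biased low for unselected stroke survivors given the same training. This needs event-prone people to be less likely to enter Aim 3. The study-wide staff withdrawal rule and self-selection make that plausible, but its size is unknown: an assumed 10% share could stay at 10% or fall to 5.3% or lower. Without an Aim 1 and 2 event table, no reader could judge which applies.

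The exclusion of voluntary withdrawals is a separate and more explicit route to the same error if it is applied to safety. The change should be made; it concerns reporting and remit, not a flaw that invalidates the trial.

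**What to change.** 1. **Section 4.0.** Keep the Aim 3 safety outcome, reported by randomised group, and label it as observed in participants with earlier vibration exposure.
2. **Sections 4.0 and 11.0.** Add a separate table of adverse events among everyone exposed to vibration in Aims 1 and 2, including anyone withdrawn. State how many did not enter Aim 3 for a safety or tolerability reason, apart from those not needed because of the cap of 44.
3. **Section 13.0.** State that withdrawn participants, voluntary or not, stay in the safety set for the data collected up to withdrawal.
4. **Section 12.0.** Give the DSMB the Aim 1 and 2 event listing at its first review and in its quarterly reports.
5. **Section 3.0.** Limit the safety goal to what these data can support.

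The cost is protocol wording, one extra table and a listing, from events that section 12.0 already requires to be recorded; reasons for not entering Aim 3 would need to be noted. No participants or procedures are added. The downside for the sponsor is a safety statement that may be less favourable and will be more modest.

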**1.0 Objectives / Specific Aims**

The objective of this project is to develop and test a method of providing real-time augmentation of hip proprioceptive feedback during post-stroke walking. Our central hypothesis is that augmented proprioception will increase the mechanics-dependent modulation of step width, an important gait stabilization strategy. The first aim of this study is to identify the physiological mechanism underlying the beneficial effects of sensory augmentation on step-by-step gait stabilization. Here, we will differentiate between the potential mechanisms of altered perception and cutaneous cueing. The second aim is to determine whether personalizing sensory augmentation methods to individual participants produces greater beneficial effects on post-stroke gait stability. Here, we will identify the optimal combination of vibration pattern and location for each participant, and test whether this personalized stimulation is superior to standard methods. The third aim is to establish the safety, feasibility, and efficacy of a rehabilitation intervention centered on repeated exposure to sensory augmentation during gait. This will be accomplished through a small-scale clinical trial.

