## 11.0 Data Management

For Aim 1, our first analysis will be correlation-based, testing whether metrics of altered perception or cutaneous cueing are associated with the beneficial effects of sensory augmentation. For each participant, we will quantify four independent variables: cutaneous detection threshold (paretic and non-paretic legs); lateral sway distance evoked by hip abductor vibration (paretic and non-paretic legs). We will also quantify the effect of sensory augmentation during gait as the mean change in paretic  $\rho_{\text{disp}}$  between the Normal and Vibrated Abductors trials ( $\Delta \rho_{\text{disp}}$ ). We will test whether each of the four independent

variables is significantly associated with  $\Delta \rho_{\text{disp}}$ , using an alpha value of 0.0125 to account for multiple comparisons. Our second analysis will involve a repeated measures experimental design – directly testing whether vibration designed solely to provide cutaneous cues (Vibrated Trunk condition) has a smaller beneficial effect than vibration designed to elicit both cutaneous cues and an altered perception of pelvis mechanics (Vibrated Abductors condition). For this analysis, we will use a repeated measures ANOVA to compare mean paretic  $\rho_{\text{disp}}$  values during the Normal, Vibrated Abductors, and Vibrated Trunk trials.

For Aim 2, our primary statistical analysis will compare the average increase in paretic  $\rho_{\text{disp}}$  values during Standard Augmentation and Personalized Augmentation conditions (relative to Normal). We will use a paired t-test to compare these  $\Delta \rho_{\text{disp}}$  values. Secondarily, we will use a repeated measures ANOVA to test for group-wide effects of vibration pattern and location, based on data from the first session.

For Aim 3, our primary statistical analysis will use an independent t-test to determine whether the change in paretic  $\rho_{\text{disp}}$  differs significantly between the Augmented and Control groups.

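### Aim 1's trunk-versus-abductor comparison isolates altered perception only if the skin cue works equally well at both sites, and detectability is measured only at the hip

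*Combined protocol and SAP*

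**What the plan says.** Section 1.0 (Objectives / Specific Aims) gives the purpose of Aim 1: "we will differentiate between the potential mechanisms of altered perception and cutaneous cueing".

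Section 10.0 (Study Design / Methods) describes one session. On detectability it says: "We will quantify the cutaneous detection threshold for vibration delivered over the bilateral hip abductors". On the walking trials it says: "In some of these trials, vibration will be applied to the hip abductors or lateral trunk, while we quantify" the gait outcome.

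Section 11.0 (Data Management) plans two analyses.

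- **Correlation analysis.** Four variables are each related to the change in paretic ρ_disp between the Normal and Vibrated Abductors trials, at alpha 0.0125. They are "cutaneous detection threshold (paretic and non-paretic legs); lateral sway distance evoked by hip abductor vibration (paretic and non-paretic legs").
- **Repeated measures analysis.** An ANOVA compares Normal, Vibrated Abductors and Vibrated Trunk. The abductor condition is defined as "vibration designed to elicit both cutaneous cues and an altered perception of pelvis mechanics (Vibrated Abductors condition"). Against that condition, the trunk condition serves as the skin-cue-only comparator, and the analysis is presented as "directly testing whether vibration designed solely to provide cutaneous cues (Vibrated Trunk condition) has a smaller beneficial effect".

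No section describes a detection threshold at the trunk, trunk and hip stimulation equated for detectability, or a detectability term in the ANOVA. The Fugl-Meyer sensation measure taken at screening covers the lower extremity only.

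**The concern.** The second analysis works by subtraction: skin cue plus altered perception, minus skin cue alone, leaves altered perception. That holds only if the skin-cue part is about the same size at the trunk and at the hip. If the trunk cue is harder to feel, pure cueing also predicts a smaller trunk effect. If it is easier to feel, it can offset a real perception effect and make the two conditions look alike.

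The plan itself gives detectability this importance. Section 11.0 uses the threshold as a metric of cueing and asks whether it explains differences between participants in the gait benefit. If it can do that between people, a threshold difference between sites could do the same between conditions. Yet it is measured at only one of the two sites compared.

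At stake is the mechanistic reading of this contrast. The test could be carried out correctly and the interpretation still be wrong.

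**Working it through.** **1. The plan's own figure.** Section 11.0 gives n = 40 to detect r = 0.5. The per-test alpha is 0.05/4 = 0.0125. Aim 1 power is not stated, so 0.80 is assumed, as in Aim 3. By Fisher's z:

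n = ((z(1 − 0.0125/2) + z(0.80)) / atanh(0.5))² + 3 = ((2.498 + 0.842) / 0.549)² + 3 = 39.96, rounded up to 40.

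The figure reproduces. It belongs to the correlation analysis; Section 11.0 gives no power statement for the trunk comparison.

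**2. What the contrast estimates.** Let C be the skin-cue benefit at the abductors, f the ratio of the trunk cue's benefit to C, and A the altered-perception benefit.

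- Abductors minus Normal: C + A
- Trunk minus Normal: f × C
- Abductors minus Trunk: A + (1 − f) × C

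The contrast equals A only when f = 1. With f below 1 it is positive even if A = 0. With f above 1 it understates A. For example, C = 1.0, f = 1.3 and A = 0.3 give 0.3 − 0.3 = 0, so a real effect disappears. Nothing planned at the trunk bears on f.

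**3. Size under pure cueing (A = 0).** n = 40 is the plan's figure. The abductor effect d, in SD units of the paired Abductors-minus-Trunk difference, and the retained share f are assumptions. The standardised paired difference is (1 − f) × d and the noncentrality is (1 − f) × d × √40. The probability is the upper tail of a noncentral t with 39 degrees of freedom beyond 2.023, which is the trunk-smaller side of a two-sided 0.05 paired test.

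| d | f | (1 − f) × d | Noncentrality | Probability of finding trunk smaller |
|---|---|---|---|---|
| any | 1.0 | 0 | 0 | 0.025 |
| 0.5 | 0.7 | 0.15 | 0.949 | 0.15 |
| 0.5 | 0.5 | 0.25 | 1.581 | 0.34 |
| 0.8 | 0.7 | 0.24 | 1.518 | 0.32 |
| 0.8 | 0.5 | 0.40 | 2.530 | 0.69 |
| 1.0 | 0.7 | 0.30 | 1.897 | 0.46 |
| 1.0 | 0.5 | 0.50 | 3.162 | 0.87 |

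The paired test stands in for the relevant pairwise contrast within the three-condition ANOVA.

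**4. What a covariate can do.** Regress D, the paired Abductors-minus-Trunk difference, on T, the trunk-minus-hip threshold difference: D = a + b × T. With T uncentred, a is the expected contrast at equal thresholds. If T is centred at its sample mean, the least-squares intercept equals the raw mean of D, so the estimate of interest is not adjusted at all. T must therefore stay uncentred.

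**The case against.** **The correlation analysis already addresses mechanism.** It sets hip threshold (cueing) and evoked sway (perception) against the abductor effect, does not use the trunk condition, and is the analysis for which n = 40 was chosen. This stands, and it confines the point to the second analysis. It does not repair that analysis, because it contains no trunk data.

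**The hip is the right site for the threshold.** For the correlations this is true, since their outcome is the response to abductor vibration. The Section 10.0 measurement is not an error. The gap is that the second analysis needs a counterpart at the trunk.

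**The confound is conjectural and could run either way.** Nothing in the documents shows that the trunk cue is less detectable or that the benefit falls with detectability. If vibration is clearly above threshold at both sites, a threshold difference need not mean a weaker cue. If the hip is the less sensitive site, the test is conservative. All this stands. The point is that the planned data cannot tell these cases apart.

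**The probabilities come from assumed inputs.** They do. The values of d and f have no source in the Aim 1 plan, and the calculation gives every participant the same f. The only effect size of 1.0 in the documents is the Aim 3 estimate. The table illustrates sensitivity and does not estimate this trial's error rate.

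**The plan never states the inference.** A reader might infer that the sponsor has committed to treating a smaller trunk effect as proof of altered perception. No sentence says so; Section 11.0 says only what is tested. The reading follows from the Aim 1 purpose together with the condition definitions, and it should be described in those terms.

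**Conclusion.** The concern holds for the second Aim 1 analysis. As planned, the trunk-versus-abductor contrast cannot separate altered perception from a site difference in how well the skin cue works, in either direction. Under pure cueing, the chance of finding a smaller trunk effect is 0.15 to 0.87 over the assumed range, against 0.025 with equal cues. That range rests on assumed effect sizes and retained shares.

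Two stronger readings are not supported. One is that Aim 1 as a whole cannot distinguish the mechanisms: the correlation analysis is a partial, independent line of evidence. The other is that the contrast is biased towards altered perception: the documents fix neither the direction nor the existence of a detectability difference.

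The change is worth making because the contrast serves the stated purpose of Aim 1 and the remedy is small. Sample size, the safety measures and the Aim 3 efficacy endpoint are unaffected. Under Section 10.0, it is the Aim 2 result that decides whether Aim 3 includes a personalisation session.

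**What to change.** 1. Repeat the existing detection-threshold test over the lateral-trunk tactor sites, on both sides, in the same Aim 1 session. Report trunk and hip thresholds side by side.
2. Keep the planned ANOVA. As a sensitivity analysis, regress each participant's Abductors-minus-Trunk difference in paretic ρ_disp on the trunk-minus-hip threshold difference. Define that difference in advance (for example, averaged over sides) and do not mean-centre it, so that the intercept is the contrast at equal thresholds.
3. If few participants have threshold differences near zero, label the intercept as an extrapolation. State also that equal thresholds do not guarantee equal perceived intensity above threshold.
4. If the trunk measurement is not added, limit the conclusion of the second analysis to a dependence of the effect on vibration site, and do not attribute it to altered perception on that contrast alone.

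The cost of items 1 to 3 is a short extra test per participant within an existing session and one pre-specified sensitivity model, with no change in sample size. Item 4 costs nothing.
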